4.1. Subject Disposition

4.1.1. Study Information

Analysis Set: All subjects who were obtained informed consent

Analysis Variables:

Analysis Methods: For the above analysis items, the following analysis is performed.

(1) Show above items.

If the last administration date of the study drug is missing, the last visit date of the study is used.

4.1.2. Subject Disposition

Analysis Set: All subjects who were obtained informed consent

Analysis Variables: All subjects who were obtained informed consent, Randomized Subjects, Full Analysis Set, Safety Analysis Set

Analysis Methods: For the above analysis items, the following analysis is performed.

(1) Tabulation of subjects included in/excluded from each analysis set

4.1.3. Eligibility of Subjects

Analysis Set: All subjects who were obtained informed consent

Analysis Variables: Eligibility for the study

[Yes, No (and the reason)]

Analysis Methods: For the above analysis items, the following analysis is performed.

(1) Calculate the number of subjects and Proportions (%).

4.1.4. Treatment Exit Status

Analysis Set: Full Analysis Set

Analysis Variables: Treatment Exit Status [Complete, Incomplete (and the reason)]

Analysis Methods: For the above analysis items, the following analysis is performed.

(1) Calculate the number of subjects and Proportions (%).

4.1.5. Protocol Deviations and Analysis Datasets

4.1.5.1. Protocol Deviations

Analysis Set: Randomized Subjects

Analysis Variables: Protocol Deviations

[Major GCP Violations, Deviations of Protocol Entry Criteria, Deviations of Discontinuation Criteria, Deviations Related to Treatment Procedure or Dose, Deviations Concerning Excluded Medication or Therapy, Deviations to Avoid Emergency Risk, Deviations Related to Efficacy Evaluation, Deviations Related to Safety Evaluation, Other Deviations]

Analysis Methods: For the above analysis items, the following analysis is performed.

Summarize the number of subjects who have deviated from the protocol, classify the deviations into above category, and show the breakdown of deviations. Subjects applicable for multiple categories will be counted once in each category.

(1) Calculate the number of subjects and Proportions (%).

4.1.5.2. Datasets for Analyses

Analysis Set: Randomized Subjects

Analysis Variables: Subjects excluded from analysis datasets [Reason of exclusion]

Inclusion of Subjects

Full Analysis Set [Adopted]

Safety Analysis Set [Adopted]

Analysis Methods: For the above analysis items, the following analysis is performed.

- (1) Calculate the number of subjects and Proportions (%) in each analysis set about handling for subjects (and reasons for exclusion). Subjects applicable for multiple categories in reason for excluded will be counted once in each category.
- (2) Calculate the number of subjects and proportions (%) of adopted subjects of each analysis set in randomized subjects.

4.2. Demographics and Other Baseline Characteristics

4.2.1. Distribution of Demographics Items

Analysis Set: Full Analysis Set

Analysis Variables:

Age (years old) [Min<= - <65, 65<= - <75, 75<= - <=Max]

Gender [Male, Female]

Height (cm)

[Min<= - <150, 150<= - <160,
160<= - <170, 170<= - <=Max]

Weight (kg)

[Min<= - <50.0, 50.0<= - <60.0,
60.0<= - <70.0, 70.0<= - <80.0,
80.0<= - <=Max]

BMI (kg/m²)

[Min<= - <18.5, 18.5<= - <25.0,
25.0<= - <=Max]

Duration of Diabetes

[3 Years or More, Less than 3 Years]

Work Status [Worker, Unemployed]

Alcohol Intake History

[Regular Drinker, Occasional Drinker, Non-Drinker]

Smoking Habits [Yes, No]

Experience of Educational Hospitalization on DM

[Yes, No]

Presence of Cohabiter

[Living Alone, Living Together]

Compliance with DPP-4 Inhibitors During 4 weeks before the Start of Treatment Period

[90 Percent or More, Less than 90 Percent]

Number of Oral Drugs per Day at the Beginning of the Treatment Period

[1 or 2 Tablet(s), 3 - 5 Tablets, 6 Tablets or More]

Complication of Metabolic Syndrome

[Yes, No]

HbA1c (NGSP) Level at the Time of Informed Consent

[<7.0%, 7.0%=<-<8.0%, 8.0%=<]

DTSQ Treatment Satisfaction Level (Except for question 2 and 3) at the Time of Informed Consent

Analysis Methods: For the above analysis items, the following analysis is performed.

- (1) Tabulation for discrete variables and summary statistics for continuous variables

4.2.2. Concurrent Medical Conditions

Analysis Set: Full Analysis Set

Analysis Variables: Concurrent Medical Conditions

Analysis Methods: For the above analysis items, the following analysis is performed.

- (1) Calculate the number of subjects and Proportions (%).

Analysis variables will be coded using the MedDRA dictionary and be summarized into SOC and PT. SOCs will be sorted in alphabetical order, then PTs will be sorted in frequency order. The method of accounting for the frequency is as follows.

[Method of Accounting for the Frequency]

Within each summary, subjects with one or more events within a level of SOC term is counted only once in that level. Similarly, subjects with one or more events within a level of PT term is counted only once in that level.

4.2.3. Prior and Concomitant Medication

Analysis Set: Full Analysis Set

Analysis Variables: Prior Medication, Concomitant Medication

Analysis Methods: For the above analysis items, the following analysis is performed.

- (1) Calculate the number of subjects and Proportions (%).
 Analysis variables will be coded using the WHO (World Health Organization) Drug and be summarized into Preferred Name. Coded medications will be sorted in frequency order. Medications used more than once within a subject will be counted only once for the subject.

5. EFFICACY EVALUATIONS

5.1. Primary Endpoint and the Analytical Methods

5.1.1. Treatment Preference (Treatment Selection Rate)

Analysis Set: Subjects in Full Analysis Set from whom preference for treatment was interviewed

Analysis Variables: Patient preference for treatment interviewed from the subjects using the standardized questions

Visit: End of Treatment Period

Analysis Methods: For the above analysis items, the following analysis is performed.

- (1) Calculate the treatment selection rate (%) for each treatment group and all subjects in the analysis set
- (2) Applying the Mainland-Gart test, the treatment selection rates for once-weekly DPP-4 inhibitor and daily DPP-4 inhibitor are compared by p-value.

Fisher's exact test for the following 2×2 table is performed and p-value will be calculated for subjects who selected either one (excluding subjects who selected "Neither good" nor "Neither wanted").

	(\times , \circ) Prefer to the second treatment.	(\circ , \times) Prefer to the first treatment.
T-A	xx	xx
A-T	xx	xx

- (3) As sensitivity analysis, performed the same analysis as (1) - (2) on the subjects in the Full Analysis Set who were administered both of Trelagliptin and Alogliptin at

least once and were interviewed the treatment preference.

5.2. Secondary Endpoints and the Analytical Methods

5.2.1. Patient Preference by Background Factors

Analysis Set: Subjects in Full Analysis Set from whom preference for treatment was interviewed

Analysis Variables: Patient preference for treatment interviewed from the subjects using the standardized questions

Visit: End of Treatment Period

Analysis Methods: For the above analysis items, the following analysis is performed.

- (1) Calculate the treatment selection rate (%) for each treatment group and all subjects in the analysis set by background factors.
- (2) Regarding the ratio (odds) of the selection rate of once-weekly dosing of DPP-4 inhibitor to the selection rate of once-daily dosing of DPP-4 inhibitor by each background factor, the odds ratio between the background factor and their both sides 95 % confidence interval are calculated for all subjects in the analysis set (treatment group are combined).

5.3. Other Endpoints and the Analytical Methods

5.3.1. DTSQ Treatment Satisfaction for Each Study Drug at 8 Weeks after Start of Each Study Drug Administration

Analysis Set: Full Analysis Set

Analysis Variables: DTSQ Treatment Satisfaction *1

DTSQ Treatment Satisfaction (each item)

Visit: 8 weeks after start of administration of each study drug

Analysis Methods: For the above analysis items, the following analysis is performed.

- (1) Calculate summary statistics for each study drug.

*1 Evaluated with the total points of questions 1, 4, 5, 6, 7, and 8

Items that refer to blood glucose levels (questions 2 and 3) are excluded in order to prevent the assessment of satisfaction from being influenced by the blood

glucose level-related part.

5.3.2. HbA1c (NGSP) for Each Study Drug at 8 Weeks after Start of Each Study Drug Administration

Analysis Set: Full Analysis Set

Analysis Variables: HbA1c (NGSP)

Visit: 8 weeks after start of administration of each study drug

Analysis Methods: For the above analysis items, the following analysis is performed.

- (1) Calculate summary statistics for each study drug.

5.3.3. Treatment Compliance for Each Study Drug at 8 Weeks after Start of Each Study Drug Administration

Analysis Set: Full Analysis Set

Analysis Variables: Treatment Compliance [Properly (90 Percent or More), Generally (70 Percent or More), Half (50 Percent or More), Less than Half (Less than 50 Percent)]

Visit: 8 weeks after start of administration of each study drug

Analysis Methods: For the above analysis items, the following analysis is performed.

- (1) Calculate the number of subjects and Proportions (%) for each study drug.

6. SAFETY EVALUATION

6.1. Brief Summary of Adverse Events (TEAE)

Analysis Set: Safety Analysis Set

Analysis Variables: TEAE

- 1) All of the TEAEs
- 2) TEAEs Related to Study Drug
- 3) TEAEs by Severity
- 4) TEAEs Related to Study Drug by Severity
- 5) TEAEs Leading to Discontinuation of Study Drug
- 6) Serious TEAEs
- 7) Serious TEAEs Related to Study Drug

8) Serious TEAEs Leading to Discontinuation of Study Drug

9) TEAEs Leading to Death

Analysis Methods: The following analyses are performed on TEAEs.

(1) Calculate the number of subjects and Proportions (%) by Study Drug.

Incidence rates will be calculated as following.

[Frequency of Subjects]

· Frequency by Severity

Subjects with one or more adverse events within a level of MedDRA term is counted only once in that level using the most severe incident. The denominator when calculating the incidence of adverse events is the number of subjects of safety analysis set.

· Analyses Other Than the Above

Subjects with one or more adverse events within a level of MedDRA term is counted only once for that MedDRA term.

The denominator when calculating the incidence of adverse events is the number of subjects of safety analysis set.

(2) For TEAE described in the CRF, prepare a replacement table for SOP and PT. SOC's will be sorted in alphabetical order, then PT's will be sorted in frequency order.

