#### 13.1.1 Analysis Sets

In this study, two analysis sets comprising the “Full Analysis Set (FAS)” and the “Safety Population” will be established. The FAS used as the main efficacy analysis set is defined as “randomized subjects who receive at least one dose of study drugs”. The safety population is defined as “subjects who receive at least 1 dose of study drugs”.

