2. ANALYSIS SET

- Full Analysis Set
The subjects who were randomized and given at least one dose of the study drug
- Safety Analysis Set
The subjects who were given at least one dose of the study drug

3. CONSIDERATIONS on STATISTICAL ANALYSIS

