6.2. Display of TEAE

Analysis Set: Safety Analysis Set

Analysis Variables: TEAE

- 1) All of the TEAEs
- 2) TEAEs Related to Study Drug
- 3) TEAEs by Severity
- 4) TEAEs Related to Study Drug by Severity
- 5) TEAEs Leading to Discontinuation of Study Drug
- 6) Serious TEAEs
- 7) Serious TEAEs Related to Study Drug
- 8) Serious TEAEs Leading to Discontinuation of Study Drug
- 9) TEAEs Leading to Death
- 10) Non-serious TEAE with Incidence of over 5%

Analysis Methods: For the above analysis items, the following analysis is performed by

Study drug.

- (1) Tabulation of frequencies of all adverse events about number of subjects, its proportions (%) and number of cases. Analysis variables will be coded using the MedDRA dictionary and be summarized into SOC and PT. SOC's will be sorted in alphabetical order, then PT's will be sorted in frequency order. Incidence rates will be calculated as following.

[Frequency of Subjects]

· Frequency (by SOC/PT)

Within each summary, subjects with one or more adverse events within a level of SOC term is counted only once in that level. Similarly, subjects with one or more adverse events within a level of PT term is counted only once in that level. The denominator when calculating the incidence of adverse events is the number of subjects of safety analysis set.

· Frequency by Severity (by SOC/PT)

Subjects with one or more adverse events within a level of SOC term is counted only once in that level using the most severe incident. Subjects with one or more adverse events within a level of PT term is counted only once in that level using the most severe incident. The denominator when calculating the incidence of adverse events is the number of subjects of safety analysis set.

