9. REVISION HISTORY

Ver.	Date	Author	Revised Content	Reason for Revision
1.0	2017/8/9	PPD	-	-
2.0	2018/3/15	PPD	
 • In order to clarify a part of the analysis content, description was adjusted. • Add description of “3.8. Time Window”. • Description in "4.1.5.2. Datasets for Analyses" was broken up into tabulation about the reasons for exclusion from analysis sets and tabulation about adopted subjects. • Add sensitivity analysis to "5.1.1. Treatment Preference (Treatment Selection Rate)" • Add creation of replacement table of adverse events to "6.1. Brief Summary of Adverse Events (TEAE)" • Revision of "7. LISTING" 	
In the process of creation of analysis result layout, some descriptions and clause titles in SAP were reconsidered so that analysis content become easy to be understood.
 
As for Time Window was added by necessity.
 
The sensitivity analysis of the treatment preference had been considered by the results of the data review and added.
 
The contents of LISTING has been revised as it has been changed to a policy that it should cyclopaedically reflect the contents of CRF.

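### Adverse events are tabulated by study drug, but the stated denominator is the whole safety set, so a subject who leaves before the switch counts under a drug never taken (minor effect)

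*SAP*

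**What the plan says.** SAP 6.1 gives the unit of tabulation as the drug: "Calculate the number of subjects and Proportions (%) by Study Drug". SAP 6.2 also tabulates by study drug. Both sections then fix the denominator: "The denominator when calculating the incidence of adverse events is the number of subjects of safety analysis set". The sentence appears four times, twice in each section.

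The safety set has one definition in each document. SAP section 2 has "The subjects who were given at least one dose of the study drug"; protocol 13.1.1 has "subjects who receive at least 1 dose of study drugs". Neither has a version by drug or by period.

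Three other places bear on the point:

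- The disposition table (SAP 4.1.2) counts "All subjects who were obtained informed consent, Randomized Subjects, Full Analysis Set, Safety Analysis Set". It does not count subjects given each drug.
- The preference sensitivity analysis in SAP 5.1.1 (3) is limited to "the subjects in the Full Analysis Set who were administered both of Trelagliptin and Alogliptin" at least once. The revision history (SAP 9) explains its origin: "The sensitivity analysis of the treatment preference had been considered by the results of the data review and added".
- Item 10 of SAP 6.2 is a table selected by a threshold: "Non-serious TEAE with Incidence of over 5" percent.

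**The concern.** Each subject takes one drug for 8 weeks and then the other for 8 weeks. Someone who leaves before the switch belongs to the safety set but was never at risk of an adverse event on the second drug. A by-drug table with the whole safety set as denominator treats that person as exposed and free of events, so the rule can only leave a drug's incidence unchanged or lower it.

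The SAP itself allows for subjects who took only one drug, because it restricts a preference analysis to those who took both. The safety section has no matching restriction. The addition of that analysis after data review is consistent with such subjects existing, but does not prove it.

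At stake are the accuracy of the per-drug incidences, the informal comparison a reader makes between the two columns, and membership of the over-5% table. Two programmers could also follow the text in good faith and produce different percentages.

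**Working it through.** **Inputs**

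- Randomized: 60, 30 per sequence (protocol 13.3).
- Planned discontinuation: 10% over the study (protocol 13.3), so 0.10 × 60 = 6 subjects. The share leaving before Week 8 is not given.
- Assumptions: all 60 are dosed, so the safety set is S = 60; between 0 and 6 subjects leave before the switch; the 5% cut in SAP 6.2 item 10 is applied to each drug separately.

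The plan gives no figure for the adverse-event denominators. Its subject numbers are consistent with each other: 54/(1 − 0.10) = 60.

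**Displayed against exposed incidence.** Let x subjects have an event on a drug and k subjects never take that drug. The rule shows x/S; the incidence among those exposed is x/(S − k). Hence

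displayed = exposed × (S − k)/S.

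| k | 0 | 1 | 2 | 3 | 4 | 5 | 6 |
|---|---|---|---|---|---|---|---|
| (60 − k)/60 | 1.000 | 0.983 | 0.967 | 0.950 | 0.933 | 0.917 | 0.900 |

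At the extreme k = 6, 3 events show as 5.0% instead of 5.6%, 6 events as 10.0% instead of 11.1%, and 12 events as 20.0% instead of 22.2%.

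**Equal exits.** Six exits split 3/3 leave 57 exposed to each drug. Take 6 affected subjects on one drug and 3 on the other:

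- exposed: 6/57 = 10.5% and 3/57 = 5.3%; difference 5.3 points, ratio 2.0;
- displayed: 6/60 = 10.0% and 3/60 = 5.0%; difference 5.0 points, ratio 2.0.

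The ratio is unchanged and the difference is multiplied by 57/60 = 0.95.

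**Unequal exits.** Let a be early exits from A-T (never took trelagliptin) and b early exits from T-A (never took alogliptin). The trelagliptin-to-alogliptin incidence ratio is multiplied by (60 − a)/(60 − b). For uneven splits, in whichever direction gives a factor above 1:

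- 2/1: 59/58 = 1.02
- 4/2: 58/56 = 1.04
- 6/0: 60/54 = 1.11

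If leaving is unrelated to sequence, the chance that all six come from one sequence, in either direction, is 2 × C(30,6)/C(60,6) = 0.024.

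**Over-5% table**, for 54 to 60 exposed:

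- 2 subjects: at most 2/54 = 3.7%, never listed;
- 3 subjects: 3/60 = 5.0%, not listed; 3/59 = 5.1% up to 3/54 = 5.6%, listed;
- 4 subjects: at least 4/60 = 6.7%, always listed.

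Only a preferred term seen in exactly 3 subjects can change status, and one early leaver is enough to change it.

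**The case against.** The strongest reply is that this is loose wording rather than a wrong rule. The SAP defines the safety set by dosing with the study drug, in the singular. Applied within each column of a by-drug table, that could mean safety-set subjects dosed with that drug, which is the correct denominator. Protocol 13.1.4 also speaks of frequency tables in the safety population for each treatment group, which suggests a population divided by column. A per-drug denominator may well be what the authors meant. But the sentence names the number of subjects in the set, the set is defined once, and a treatment group may mean a sequence rather than a drug. Neither passage supplies a per-drug number.

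Other parts of the reply stand:

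- SAP section 6 plans no ratio, difference, interval or test between drugs, so the figures on ratios and differences concern only what a reader may infer.
- Counts are displayed, and the exit-status table (SAP 4.1.4) and discontinuation listing (SAP 7) would help a reader work out exposure.
- The threshold effect depends on all 60 being dosed. With a safety set of 59, 3/59 = 5.1% is listed under either denominator. Two subjects would exceed 5% only with fewer than 40 in the denominator.
- The SAP does not say whether the 5% cut applies to each drug or overall.
- Exits after the switch have no effect, so six early exits is an upper bound.

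These points limit the size of the problem; they do not put the missing denominator into the text.

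**Conclusion.** The concern holds. As written, the denominator in SAP 6.1 and 6.2 includes subjects who never took the drug being tabulated, and nothing elsewhere in the documents corrects it. Under the stated assumptions, a drug's incidence is understated by 0 to 10% in relative terms: 5% for both drugs if six early exits split evenly, and nothing if nobody leaves before the switch. The ratio between drugs is distorted only when early exits differ by sequence. One table's content can change, for a term seen in exactly 3 subjects, and that term would still appear with its count in the table of all events. The effect is therefore minor. No test or decision rests on these rates. The correction is worth making because the rule is explicit, errs only towards lower incidence, and costs almost nothing to repair.

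**What to change.** Replace all four denominator statements in SAP 6.1 and 6.2 with: *The denominator for each study drug is the number of subjects in the safety analysis set who took at least one dose of that drug.* Show that number in each column header.

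An optional addition, separate from the error, is one sentence saying that an event is tabulated under the drug being taken at onset. This fits the protocol's start-date rules (10.1.7), the start date recorded for each event (10.2.1.2) and its treatment of a worsening after a change of study drug as a new event (10.1.2).

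The cost is SAP wording and a column-header count, with no new data and no protocol revision. Per-drug incidences stay the same or rise slightly.

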6.2. Display of TEAE

Analysis Set: Safety Analysis Set

Analysis Variables: TEAE

- 1) All of the TEAEs
- 2) TEAEs Related to Study Drug
- 3) TEAEs by Severity
- 4) TEAEs Related to Study Drug by Severity
- 5) TEAEs Leading to Discontinuation of Study Drug
- 6) Serious TEAEs
- 7) Serious TEAEs Related to Study Drug
- 8) Serious TEAEs Leading to Discontinuation of Study Drug
- 9) TEAEs Leading to Death
- 10) Non-serious TEAE with Incidence of over 5%

Analysis Methods: For the above analysis items, the following analysis is performed by

Study drug.

- (1) Tabulation of frequencies of all adverse events about number of subjects, its proportions (%) and number of cases. Analysis variables will be coded using the MedDRA dictionary and be summarized into SOC and PT. SOC's will be sorted in alphabetical order, then PT's will be sorted in frequency order. Incidence rates will be calculated as following.

[Frequency of Subjects]

· Frequency (by SOC/PT)

Within each summary, subjects with one or more adverse events within a level of SOC term is counted only once in that level. Similarly, subjects with one or more adverse events within a level of PT term is counted only once in that level. The denominator when calculating the incidence of adverse events is the number of subjects of safety analysis set.

· Frequency by Severity (by SOC/PT)

Subjects with one or more adverse events within a level of SOC term is counted only once in that level using the most severe incident. Subjects with one or more adverse events within a level of PT term is counted only once in that level using the most severe incident. The denominator when calculating the incidence of adverse events is the number of subjects of safety analysis set.

